3.2. Study Design Rationale

Vaccines and Dose Selection Rationale

The rationale behind selection of study vaccines and doses is described in Section 1.1.

Blinding, Control, Study Phase/Periods, Treatment Groups

A placebo control will be used to establish the frequency and magnitude of changes in clinical endpoints that may occur in the absence of active treatment. Randomization will be used to

minimize bias in the assignment of subjects to treatment groups, to increase the likelihood that known and unknown subject attributes (eg, demographic and baseline characteristics) are evenly balanced across treatment groups, and to enhance the validity of statistical comparisons across treatment groups. Blinded treatment will be used to reduce potential bias during data collection and evaluation of clinical endpoints.

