6. DOSAGE AND ADMINISTRATION

Each subject will receive study vaccine/placebo at 4 time points according to randomization, on Day 1 and Weeks 12, 24, and 48, administered by IM injection into the deltoid. For visits with

only one injection (ie, at Weeks 0 and 12), preferably the deltoid of the non-dominant upper arm is used. When 2 injections are to be given at one visit (ie, at Weeks 24 and 48), it is required to use a different deltoid for each injection. Exceptions on injection site are allowed only if medically indicated.

For information on vaccination windows, see Section 9.1.2. If a subject cannot be vaccinated within the allowed window, then that vaccination should not be administered. However, if the window is missed due to a study pause (see Section 11.9), vaccination will be assessed on a case-by-case basis, upon discussion between sponsor and investigator. If a subject misses more than one study vaccination, he/she will be withdrawn from further study vaccination (see Section 10.4). Study vaccines are as follows:

- Ad26.Mos4.HIV:
Total dose is 5×10^{10} vp per 0.5 mL injection
- Ad26.Mos.HIV:
Total dose is 5×10^{10} vp per 0.5 mL injection
- Clade C gp140:
Clade C gp140 with 250 mcg total protein, mixed with aluminum phosphate adjuvant (0.425 mg aluminum) at the pharmacy, per 0.5 mL injection
- Placebo:
0.9% saline, 0.5 mL injection

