## DEFINITION OF TERMS

Randomization	5:1:10:2 ratio			
Study vaccine	
 
- Ad26.Mos4.HIV (Ad26.Mos.1.Env + Ad26.Mos.2.Env +Ad26.Mos1.Gag-Pol + Ad26.Mos2.Gag-Pol): Total dose is <math>5 \times 10^{10}</math> viral particles (vp) per 0.5 mL injection
 
- Ad26.Mos.HIV (Ad26.Mos.1.Env + Ad26.Mos1.Gag-Pol + Ad26.Mos2.Gag-Pol): Total dose is <math>5 \times 10^{10}</math> viral particles (vp) per 0.5 mL injection
 
- gp140 DP: gp140 DP with 250 mcg total protein, mixed with aluminum phosphate adjuvant (0.425 mg aluminum) at the pharmacy, per 0.5 mL injection
 
- Placebo: 0.9% saline, 0.5 mL injection
 
			
Vaccination compliance	Each vaccine administered (if applicable) according to planned schedule			
Vaccine regimen	Group	Planned N	Day 1, Week 12	Week 24, Week 48
	1A	55	Ad26.Mos.HIV	Ad26.Mos.HIV + gp140
	1B	11	Placebo	Placebo + Placebo
	2A	110	Ad26.Mos4.HIV	Ad26.Mos4.HIV + gp140
	2B	22	Placebo	Placebo + Placebo

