**Table 3: Phase and Period Definitions**

Phase	Phase number	Period	Period number	Interval	
				From	To
Screening	1			00:00 of the date of signing the informed consent form a	One minute prior to Dose 1 on Day 1
Regimen	2	Post-Dose 1	1	Date and time of Dose 1 (Day 1)	Minimum of: a) Maximum (28 days after first vaccination at 23:59, scheduled visit 4 weeks after first vaccination at 23:59) b) 23:59 at the date of last contact (for early discontinuation)

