### **5. SAFETY**

The safety and tolerability endpoints are:

- Unsolicited AEs 28 days following each vaccination
- Solicited local and systemic AEs (reactogenicity), collected daily from day of vaccination for 7 days post-vaccination (day of vaccination and the subsequent 7 days).

The safety and tolerability analysis will be performed on the FA set. Specifically, the analysis for solicited adverse events will be done on those subjects in the FA set for whom reactogenicity assessments are available in the database (either via on-site assessments or via the diary pages of the CRF).

Safety data will be tabulated per period by regimen. Only the active periods will be shown in the tables (AE, Lab, VS), except for SAEs. In addition, for a selection of tables (AE, Lab), tabulations per subject by vaccine and per dose by vaccine will be provided.

In the ‘per subject by vaccine’ analysis, the safety will be presented per periods (post-dose 1, 2, 3, 4) by vaccine rather than by regimen. A ‘post any dose’ period (= regimen phase in section 2.1) will be added, that summarizes the safety after all administered doses of a vaccine. The post-any-dose period allows determining how many subjects reported events after administration of a certain vaccine regardless the number of doses. Each subject is counted only once. In case a subject has the same event after more than one dose, it is counted only once (and in case of showing attributes,

the worst corresponding attribute is shown) in the post-any dose period. The denominator is the number of subjects that received the considered vaccine in the considered period.

In the ‘per dose by vaccine’ analysis, the safety will also be presented by vaccine. This table allows determining the incidence of events per administered dose of a certain vaccine. For example, if a subject has the same event at least once after dose 1 and at least once after dose 2 of the same vaccine, it is counted 2 times (so the numerator is the sum of post-dose 1, 2, 3 and 4 events in the “per subject by vaccine” table). In case of showing attributes, the worst corresponding attribute of each period are shown. The denominator is the total number of doses administered of the considered vaccine over all subjects.

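### The post-any-dose column of the by-vaccine safety tables is defined by a phase that starts before gp140 is given, so its gp140 and placebo figures are not comparable

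*SAP*

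**What the plan says.** SAP Section 5 tabulates safety per period by regimen. For a selection of adverse event and laboratory tables it adds two by-vaccine displays, one per subject and one per dose. The per-subject display shows each post-dose period and a pooled post-any-dose period, described as "regimen phase in section 2.1) will be added, that summarizes the safety after all administered doses of a vaccine". The SAP says that this period "allows determining how many subjects reported events after administration of a certain vaccine regardless the number of doses". On counting it says "Each subject is counted only once", and on the divisor "The denominator is the number of subjects that received the considered vaccine in the considered period".

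In SAP Table 3 the regimen phase consists of the four post-dose periods, and the first of them runs from "Date and time of Dose 1 (Day 1", closing bracket omitted).

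On dosing, Protocol Section 6 states: "Each subject will receive study vaccine/placebo at 4 time points according to randomization, on Day 1 and Weeks 12, 24, and 48". In the SAP's Definition of Terms, gp140 appears only in the Week 24 and Week 48 column (for Group 2A, "Ad26.Mos4.HIV + gp140"). The Day 1 and Week 12 column is Ad26 alone. The placebo groups receive saline at all four visits.

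SAP Section 5 also gives an attribution rule for the two-injection visits. Local reactions go to the product injected at that site where the link is known, and to both products where it is not. Systemic solicited and unsolicited events go to both products.

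**The concern.** A once-per-subject count over several windows rises with the number of windows. The post-any-dose column pools two windows for gp140 and four for placebo, and dividing by subjects does not correct for that. The regimen-phase definition creates a second problem. A programmer who follows it will put Ad26-only periods into the gp140 column, while one who follows the rest of the sentence will not. The table does not tell the reader which was done.

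Safety and tolerability is a primary objective, and Protocol Section 3.2 says of the control arm: "A placebo control will be used to establish the frequency and magnitude of changes in clinical endpoints". Readers will therefore tend to set the gp140 and placebo figures side by side. This is also the only place where SAP Section 5 specifies a pooled, once-per-subject incidence by vaccine. The single-period and per-dose results do not supply that quantity.

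**Working it through.** **1. Check of the formula.** The plan gives no figure for this column. The nearest is the table in Protocol Section 11.3, which uses P(at least one) = 1 − (1 − p)^n. At p = 1% and n = 110 this is 1 − 0.99^110 = 66.9%, against a stated 67%. Below, the same form is applied across k windows within a subject.

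**2. Windows per completer** (SAP Definition of Terms, Table 3 and Section 5).

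| | gp140 | Placebo |
|---|---|---|
| Post-dose windows | 2 (Post-Dose 3, 4) | 4 (Post-Dose 1 to 4) |
| Diary days, solicited events | 2 × 8 = 16 | 4 × 8 = 32 |
| Nominal days, unsolicited events | 2 × 28 = 56 | 4 × 28 = 112 |

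**3. By-vaccine reading, no true difference.** The per-window risk p is an assumption, equal in both columns. With independent windows, incidence is 1 − (1 − p)^2 for gp140 and 1 − (1 − p)^4 for placebo. For within-subject correlation ρ, a beta-binomial is used: P(no event in k windows) is the product over j = 0 to k − 1 of (b + j)/(s + j), with s = (1 − ρ)/ρ and b = (1 − p)s.

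| p | gp140, independent | Placebo, independent | Ratio, ρ = 0 | Ratio, ρ = 0.3 | Ratio, ρ = 0.6 |
|---|---|---|---|---|---|
| 10% | 19.0% | 34.4% | 0.55 | 0.67 | 0.79 |
| 20% | 36.0% | 59.0% | 0.61 | 0.71 | 0.81 |
| 30% | 51.0% | 76.0% | 0.67 | 0.75 | 0.83 |

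Worked cell, p = 20% and ρ = 0.6: s = 0.667 and b = 0.533. For two windows, P(none) = (0.533 × 1.533)/(0.667 × 1.667) = 0.736, so incidence is 26%. For four windows, P(none) = 0.736 × (2.533/2.667) × (3.533/3.667) = 0.674, so incidence is 33%. At ρ = 0.3 the pair is 31% and 44%.

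**4. By-vaccine reading, true doubling.** With per-window risk 10% for gp140 and 5% for placebo, and independent windows, the column shows 1 − 0.90² = 19.0% and 1 − 0.95⁴ = 18.5%, a ratio of 1.02.

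**5. Literal regimen-phase reading.** Assume 20% in the Ad26-only windows and 10% in the gp140-visit and placebo windows. The gp140 column shows 1 − 0.8² × 0.9² = 48.2%, although its own two windows give 19.0%. Placebo shows 34.4%. Under these rates this error runs in the opposite direction to step 3.

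**6. Effect of co-administered Ad26.** Suppose gp140 is inert, systemic risk at an Ad26 visit is 30%, and placebo risk is 10%. On the by-vaccine reading the gp140 column shows 1 − 0.7² = 51%, against 34.4% for placebo. With 20% at Ad26 visits it is 36% against 34.4%. For events booked under both products, the net direction therefore depends on rates that the documents do not give.

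**7. Matched windows.** With both columns limited to Post-Dose 3 and 4 and p = 10%, both show 19.0%, a ratio of 1.00.

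**The case against.** The strongest reply is that this is one column of an additional, descriptive table. The main safety tables are per period by regimen, where active and placebo windows match. The by-vaccine table also shows Post-Dose 3 and Post-Dose 4 separately, and the per-dose table divides by doses given. Protocol Section 11.5 plans no safety testing, and no contrast of gp140 with placebo is named. The SAP describes the column as counting events whatever the number of doses, so cumulative incidence over each vaccine's own exposure is a legitimate descriptive quantity. All of this stands, and it limits the point to a minor one.

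The reply is also right that the literal reading sits badly with the SAP's own wording about events after a vaccine was administered. That reading is better treated as an ambiguity to remove than as the intended analysis.

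A reader might infer that an inert gp140 would generally look safer than placebo. The documents do not support that. The attribution rule in SAP Section 5 loads Ad26's systemic and unsolicited events onto gp140 at Doses 3 and 4, and step 6 shows that this can reverse the sign. The inference holds only for local reactions linked to the gp140 injection site.

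The reply does not remove the contradiction in the definition. Nor does it make the gp140 and placebo entries in this column comparable under either reading.

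**Conclusion.** The point holds for the post-any-dose column of the per-subject by-vaccine tables, at minor severity. Equating that column with the regimen phase is wrong for gp140. The by-vaccine reading that remains compares two windows with four.

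The ratios of 0.55 to 0.67, rising to about 0.8 at a correlation of 0.6, rest on an assumed equal per-window risk of 10 to 30% and leave out any Ad26 contribution. They show how far the column could mislead for site-linked local reactions and are not predictions of this trial's results.

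A reader might go further and conclude that the comparison of harms between gp140 and placebo, or the safety assessment as a whole, is biased. That is not shown, because the by-regimen, single-period and per-dose results are not affected by this mismatch.

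**What to change.** In SAP Section 5:

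- Delete the equation with the regimen phase for the by-vaccine tables. Define post-any-dose for each vaccine as the post-dose periods in which that vaccine was given, which for gp140 means Post-Dose 3 and Post-Dose 4.
- Add a placebo column for any of Doses 3 and 4, with subjects given placebo at Dose 3 or Dose 4 as the denominator, to be read beside gp140. Keep the four-dose placebo column for reading beside Ad26.
- Footnote that gp140 systemic and unsolicited events include those of co-administered Ad26. Matching the windows does not isolate gp140.
- State which definition was programmed in the existing outputs.

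SAP Section 1 says that the Week 72 analysis has been done and will not be rerun, so this should be a supplementary table. The cost is a short text change and one extra column built from existing period flags. The matched placebo column rests on at most 11 + 22 = 33 subjects, fewer if some stopped before Dose 3.

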## **5.1. Adverse Events**

The analysis of AEs will be based on the MedDRA coded terms as provided in the clinical database.

### **5.1.1. Definitions**

Solicited AEs shown in the tables are extracted from the diary pages of the CRF. For unsolicited AEs, only the AEs within the 28-day period following each vaccination will be presented in the safety tables except for SAE and AESI (AE of special interest), which will be captured and tabulated in the outputs covering the whole study period. All other collected unsolicited adverse events will be presented through listings.

Solicited local AEs will be by definition considered as related to the study vaccine.

The severity of the AEs will be classified as grade 1 to 4. Solicited events that are graded less than grade 1, are not considered as AE. In case no grades are available, the grading of the solicited events will occur according to the grading list in attachment 1 of the CTP.

### **5.1.2. Analysis of Adverse Events**

Number and percentage of subjects with at least one particular AE (unsolicited/solicited) will be tabulated. Unsolicited AEs will be summarized by System Organ Class and Preferred Term. Solicited AEs will be summarized by class (local, systemic) and preferred term.

For solicited AEs following tables will be provided: summary, by worst severity grade, grade 3, related (systemic only), time to onset (in days) and duration (in days) for most frequent events and body temperature. Note: Duration is defined as number of days from the start of the event until

resolution of the event. The time to first onset is defined as (date of first onset – reference date + 1). The reference date is the start date of the vaccination period.

For unsolicited AEs following tables will be provided: summary table (including SAE, fatal outcome, AESI and discontinuation), all events, most frequent, grade 3, permanent stop of vaccine, related, SAE and AESI.

Listings and/or subject narratives will be provided as appropriate, for those subjects who die, discontinue study vaccinations due to an AE, or experience a severe or serious AE.

### **5.1.3. Transforming On-site Assessments and Diaries of Solicited Adverse Events into an Analysis Format**

Solicited events are always allocated to the respective Post Dose period.

When creating the analysis dataset for solicited AEs (dataset ADAESOL), solicited AEs (recorded by day) need to be converted into the format of unsolicited AEs (recorded by event). For this purpose, the start date of the AE will be considered as the date of first occurrence of the solicited AE (both local and systemic). If on subsequent day(s), the same grade is reported, the last reported date is used as the end date of the AE. A new record is created in case the grade of the event changes. If there is a time gap of at least 1 day between 2 (or more) occurrences of the particular solicited AE, then the second (and/or next) occurrence will be considered as a new AE. In case no data is reported for a day, this is analyzed as no event reported. If the on-site assessment differs in grade or relatedness with a corresponding day (eg, day of vaccination) of diary data, the on-site assessment should be recorded as a separate record in the database. The following example shows how the solicited AE should be converted into a format of unsolicited AEs:

#### **Data from the Subject Diary**

Subject: 0001

Solicited systemic AE: Headache

		Diary Data								
Solicited AE	On-site Assessment	Day 1 01Jan16	Day 1 01Jan16	Day 2 02Jan16	Day 3 03Jan16	Day 4 04Jan16	Day 5 05Jan16	Day 6 06Jan16	Day 7 07Jan16	Day 8 08Jan16
Grade	2	1	1	0	3	3	1	0	0	0
Relatedness	Doubtful				Probable					
Serious					N					
Outcome					Recovered/Resolved					

The data should be converted and stored in the AE dataset as follows:

Subject No.	AE	Start Date	Stop Date	Severity	Relatedness	Serious	Outcome	AEID
0001	Headache	01JAN16	01JAN16	2	Doubtful			1

0001	Headache	01JAN16	02JAN16	1	Probable	N	Recovered/Resolved	1
0001	Headache	04JAN16	05JAN16	3	Probable	N	Recovered/Resolved	1
0001	Headache	06JAN16	06JAN16	1	Probable	N	Recovered/Resolved	1

If a solicited AE ends after Day 8:

- The stop date of the event is the “Date of last day of symptom” as recorded in the eCRF and the “maximum severity” after Day 8 as recorded in the CRF. A separate record is created for this, in case this severity deviates from the previous record.

**Note:** To complete the start and end-date based on diary data, the date will be calculated based on the actual day that the AE occurred relative to vaccination and not on the reported date. For example, if the vaccination is on 01-JAN-2016, and the AE starts on Day 3, the start date will be set to the 03-JAN-2016, independent of the reported actual date.

For the calculation of duration, the first and last day is used, irrespective of whether interruptions occurred in between by missing reporting days or Grade 0 events. In the above example, the 4 records contribute to the same AE, therefore AEID is set to the same value and the duration of the AE is set to 6 for all records.

#### Step 1: Allocation of events to the periods:

Adverse events in the SDTM database are allocated to periods based on their start date/time. If the start date/time of an event falls between (or on) the start and stop date/time of a period, the AE is attributed to that period (treatment-emergent principle).

- In case of partial start or stop dates (i.e. time and/or day and/or month and/or year missing), the events are allocated to the periods using the available partial information on start and end date; no imputation will be done. If, for instance, the AE start date only month and year are available, these data are compared to the month and year information of the periods. This rule may lead to multiplication of the event as a consequence of its assignment to multiple periods.
- In case of a completely missing end date, the date is imputed by the cut-off date of the analysis for subjects still ongoing in the study, and by the end date of the last period for subjects who discontinued or completed the trial.

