#### Step 2: Combination of events:

Overlapping/consecutive events are defined as events of the same subject with the same preferred term which have at least 1 day overlap or for which the start date of an event is 1 day after the end date of the preceding event. Overlapping/consecutive events may be combined into one AE or not, according to the following rules:

- 1) If overlapping/consecutive events start in one of the following periods - Screening or post dose extension (i.e. non-active periods) - followed by an AE in - post-dose period (active period) - they are allocated to their respective periods and are considered as separate events.
- 2) In case overlapping/consecutive events start within a single period, they are considered as one and the same AE. The individual events which contribute to this AE are retained as individual

records in the ADaM database but are assigned the same onset, period, and total duration. All related attributes to the AE/phase/period should also be consistent with the new event.

3) In case overlapping/consecutive events start in both an active period followed by a non-active period, they are allocated to the active period only and are considered as one and the same AE. The individual events which contribute to this AE are retained as individual records in the ADaM database but are assigned the same onset, treatment period, and total duration. All related attributes to the AE/phase/period should also be consistent with the new event.

4) In case an active period is followed by another active period, and the overlapping/consecutive events start in both periods, they are allocated to their respective period and are considered as separate AEs. The same rule applies for 2 non-active periods.

Remarks:

1. Events can only be combined into one and the same AE if their start and stop dates are known.
2. In case the completely missing end date is imputed (for period allocation), this date is also considered as a complete date.
3. Time is not considered when determining overlap of events.

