#### **5.1.4. Handling of Missing Data for Adverse Events**

Missing data will not be imputed. Subjects who do not report an event will be considered as subjects without an event. The analysis of the solicited AEs will include only documented safety data (i.e. in case severity is missing it is not considered an event).

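### SAP 5.1.3 fills in a missing AE end date and treats it as known, contrary to 5.1.4, so a dose-1 reaction lasting past Day 8 with no recorded end can be given about 505 or 365 days

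*SAP*

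**What the plan says.** SAP 5.1.3 describes how diary and on-site records of solicited reactions become analysis records. Step 1 allocates events to study periods by start date. It then adds a rule for end dates: "In case of a completely missing end date, the date is imputed by the cut-off date of the analysis for subjects still ongoing", and "by the end date of the last period for subjects who discontinued or completed the trial" in all other cases.

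Step 2 combines overlapping or consecutive events that share a subject and a preferred term, and assigns the combined records one onset and one total duration. Remark 1 allows this only where start and stop dates are known. Remark 2 qualifies it: "In case the completely missing end date is imputed (for period allocation), this date is also considered as a complete date".

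Two other parts of the SAP point the other way:
- Section 5.1.4, on missing AE data: "Missing data will not be imputed". It adds that solicited AEs are analysed from documented data only.
- Section 5.1.2 plans tables of "time to onset (in days) and duration (in days) for most frequent events" for solicited AEs. It counts duration from the start of the event to its resolution.

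For a solicited reaction still present after Day 8, 5.1.3 takes the stop date from an eCRF field for the last symptom day. It gives no specific rule for a blank field.

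**The concern.** A cut-off date or period end is not a resolution date. If it is used as one, the duration reflects the study calendar and not the reaction. For a subject still in the study, the same reaction also grows longer at each later cut-off.

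The treatment of missing dates is also inconsistent. Step 1 leaves a partial date unimputed, so Remark 1 appears to bar that event from combination. An event with no end date at all is let through by Remark 2.

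Solicited AEs are part of the primary endpoint (protocol 2.1.2), and their duration is a planned summary (protocol 11.5, SAP 5.1.2). As the text stands, two programmers could each follow the SAP and produce different duration tables.

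**Working it through.** **Inputs**
- Dose days 1, 85, 169 and 337, and the Week 72 visit on Day 505 ± 3 weeks (protocol 9.1.2).
- Post-dose periods last 28 days after the dose, or to the scheduled 4-week visit if later (SAP Table 3). On planned days, Post-Dose 4 ends on Day 337 + 28 = 365.
- Follow-Up 4 is intended to end at Week 72 (SAP Table 3, note c).
- Duration convention: "For the calculation of duration, the first and last day is used".

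**Reproducing the SAP's own figure.** The headache example in 5.1.3 runs from 1 to 6 January. Counting inclusively, 6 − 1 + 1 = 6 days, which is the SAP's figure.

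**Duration given to a reaction that starts on the vaccination day and has no end date.** Duration = imputed end − start + 1.

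| Dose | Start day | Last period ends at Week 72 (Day 505) | Last period is Post-Dose 4 (Day 365) |
|---|---|---|---|
| 1 | 1 | 505 | 365 |
| 2 | 85 | 421 | 281 |
| 3 | 169 | 337 | 197 |
| 4 | 337 | 169 | 29 |

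Over the Week 72 visit window the dose-1 value is 484 to 526 days. A dose-1 reaction starting on diary Day 8 gives 505 − 8 + 1 = 498. For a subject still ongoing at a cut-off, a reaction starting on Day 1 runs to at least Day 197 at the Week 28 analysis and at least Day 365 at the Week 52 analysis, on planned visit days. A Group 2A subject already in the LTE at the Week 72 cut-off could exceed 505.

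**Effect on a mean.** With n events of typical mean m and one imputed value d, the mean is ((n − 1)m + d)/n. The values of n and m are assumptions, because the documents give neither.
- n = 100, m = 2, d = 505: (198 + 505)/100 = 7.0 days
- n = 20, m = 3, d = 505: (57 + 505)/20 = 28.1 days
- n = 100, m = 2, d = 365: (198 + 365)/100 = 5.6 days
- n = 20, m = 3, d = 365: (57 + 365)/20 = 21.1 days

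**Effect on combination.** Take a reaction starting on Day 2 with imputed end Day 505, and a later event of the same preferred term.
- Day 20 (Post-Dose 1): combined under rule 2.
- Day 50 (Follow-Up 1): combined under rule 3 and given the post-dose onset.
- Days 90, 170 and 340 (Post-Dose 2, 3 and 4): separate under rule 4.
- Days 130, 250 and 400 (Follow-Up 2, 3 and 4): combined only if rule 3 is read to reach across intervening doses.

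Had the true end been Day 9, none of these would be combined. An event with a different preferred term is never combined.

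**The case against.** The strongest reply is that the rule was not meant for solicited durations. Step 1 speaks of AEs in the SDTM database. Solicited events are always placed in their own post-dose period and so need no allocation step. Remark 2 gives period allocation as the purpose of the imputation. Through Day 8 the diary itself supplies the end date, so only a longer reaction with a blank eCRF field is exposed. This narrows the problem but does not remove it. Steps 1 and 2 sit inside the solicited-AE section, contain the only rule for a missing end date, and feed an assigned total duration. Nothing bars the imputed date from the duration table.

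Four stronger inferences are tempting, and the documents do not support them:
- *That 505 days is the figure.* Table 3 gives period numbers only to Post-Dose 1 to 4, so the last period may be Post-Dose 4. The SAP also uses the word loosely for follow-up phases, so both readings are open.
- *That the reaction absorbs unrelated later events.* Combination needs the same preferred term, and events starting in later post-dose periods stay separate. The SAP also does not say whether Step 2 runs across solicited and unsolicited records.
- *That late SAEs would be shown as post-dose events.* That needs the broad reading of rule 3 and a matching preferred term. More than 28 days after a dose, collection is limited mainly to SAEs, AESIs, AEs leading to discontinuation and AEs ongoing at the next dose. Individual records are retained, and listings or narratives are planned for serious events.
- *That the imputed date has no role in allocation.* With a complete start date it has none. For partially dated events, however, Step 1 uses information on both start and end.

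It is also fair that SAP 5.1.2 names no statistic for duration. A median would hardly move, and in a categorical table the event would fall in the longest category.

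**Conclusion.** The conflict is real: 5.1.3 imputes a completely missing end date and counts it as complete, while 5.1.4 forbids imputation and 5.1.2 measures duration to resolution. Followed as written, a solicited reaction continuing past Day 8 with a blank last-symptom date can be assigned hundreds of days. After dose 1 that is about 505 or about 365, depending on what the last period is. It can also be merged with a same-term event in its own post-dose period or the follow-up phase after it.

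The damage is confined to descriptive duration and some event counts. Subject-level incidence by period rests mainly on start dates and is largely unaffected, and no hypothesis test is involved. The shift in means rests on assumed event counts, an assumed typical duration and one assumed blank field. The documents do not show how many blanks there were, and there may have been none.

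SAP section 1 says the Week 72 analysis was already done and will not be rerun. Solicited AEs fall wholly within it, so the remaining value lies in clear rules and in knowing whether the finished tables were affected.

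**What to change.** 1. In SAP 5.1.3, state that an imputed end date is not used for duration or for combining events.
2. Report the duration of such an event as at least n days, counted to the last documented symptom day and flagged as ongoing or unknown. Give the number of such events beside the table.
3. Reword Remark 2 so that an imputed date does not count as a known stop date, and align 5.1.4 so that it states what, if anything, the imputation is still used for.
4. For the finished Week 72 analysis, state how many solicited-AE end dates were imputed. If there were any, add a sensitivity listing of durations without them. If there were none, a sentence saying so is enough.

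The cost is a few lines of SAP text, one count and possibly one listing. The downside is that a few events will show a minimum instead of an exact duration.
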